The total duration of study participation for each subject only participating in the placebo-controlled period of the study will be up to approximately 102 weeks, including a series of Screening visits within 8 weeks before administration of the first dose, a 76-week placebo-controlled treatment period, and a safety follow-up (FU) period of approximately 18 weeks after the final dose. The total duration of study participation for each subject participating in the placebo-controlled period and the LTE period will vary and be up to approximately 362 weeks, including a series of Screening visits within 8 weeks before administration of the first dose, a 76-week placebo-controlled treatment period, a 4-week FU period, a 256-week aducanumab dose-blind treatment period, and a safety FU period of approximately 18 weeks after the final dose.

Investigators, study site staff (except for the designated unblinded pharmacist/technician), and study subjects will be blinded to the subjects' randomized treatment assignment for the placebo-controlled period. During the LTE period, investigators and subjects will remain blinded to the treatment assignment in the placebo-controlled period and the aducanumab dose for the LTE period.

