ARIA-H superficial siderosis	Asymptomatic ARIA-H (Superficial Siderosis) Symptomatic ARIA-H (Superficial Siderosis)	superficial siderosis of the central nervous system	superficial siderosis of the central nervous system

For any specific ARIA event, the start date of the duration based on MRI is the date of the MRI assessment that initially identifies the ARIA event, and the end date of the duration based on MRI is the date of the MRI assessment that shows the complete resolution of this ARIA event (in the case of ARIA-E), or the date of the MRI assessment that shows ARIA being stable (in the case of ARIA-H). Stable was defined as 'No change' or 'decrease' in number, size, severity or number of locations between 2 consecutive MRIs including the initial detection MRI and the follow-up MRIs.

For symptomatic ARIA events, if there is any related symptom that proceeds the first MRI identification, then the symptom onset date will be used as the start date of the symptomatic ARIA duration. The end date of the symptomatic ARIA duration will be the date of the resolution or stable MRI as defined above for the duration based on MRI.

If the severity increases, or the event changes from asymptomatic to symptomatic, or from non-serious to serious, more than one AE records will be added to eCRF to capture the change with new start/end AE dates (the end date of the previous record will be the start date of the next record). For analysis, records with changes in severity or symptomatic status or seriousness are considered as a single ARIA event. The severity/symptomatic status/seriousness for that event is defined as the worst level among all the AE records that belong to that event.

If the same type of ARIA event happens again after the previous event has ended, then it is considered a recurrent event of ARIA of that type. Recurrent events will be referred as the second event, the third event, and etc.

If the duration based on MRI of an ARIA-E event overlaps with the duration based on MRI of an ARIA-H event, then these 2 ARIA events are considered as concurrent events.

Final V1.0

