4.5.3.3 Summary of recurrent ARIA-E

Follow-up adjusted incidence rate of subjects with ARIA-E, with 2 or more events of ARIA-E, with 3 or more events of ARIA-E and with more than 3 events of ARIA-E based on their entire follow-up time will be summarized based on AE eCRF. The entire follow-up time is from the first dose until the last day in the placebo-controlled period.

Number of total ARIA-E events and the MRI severity of each event will be summarized based on AE eCRF. Number of total symptomatic ARIA-E events, the MRI severity of each symptomatic event and the severity of the symptoms of each symptomatic event will be summarized based on AE eCRF.

Summary of first ARIA-E events table based on AE eCRF will summarize the number of subjects with a first event of ARIA-E, the MRI severity of the events, the symptomatic status of the events, the severity of the symptoms for symptomatic events, whether SAE or not, number of resolved and unresolved events, duration of the resolved events, time from first infusion in study (active or placebo) to onset, number of doses received since the start of the study to onset, dose level of the last infusion received prior to onset, dosing status (continue as planned, dose interrupted, dose reduced, or dose discontinued) after the events, and the number of subjects with recurrent ARIA-E events. The same summary of first ARIA-E events table will also be done on subjects who had recurrent ARIA-E events.

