Summary of recurrent ARIA-E events table based on AE eCRF will summarize the following information for both the second and third event of ARIA-E events: the number of subjects with the previous event of ARIA-E, the number of subjects with at least one dose and one MRI after the previous ARIA-E resolution, the number of subjects with this event of ARIA-E, the MRI severity of the events, the symptomatic status of the events, the severity of the symptoms for symptomatic events, whether SAE or not, number of resolved and unresolved events, duration of the resolved events, time from first infusion in study (active or placebo) to onset, time from previous resolution to onset, number of doses received since the start of the study to onset, dose level of the last infusion received prior to onset, dosing status (continue as planned, dose interrupted, dose reduced, or dose discontinued) after the events. The number of subjects with more than 3 events of ARIA-E, and the number of subjects who discontinued study treatment after recurrent ARIA-E onset will also be summarized.

A listing of subjects who withdrew from the study with unresolved ARIA-E or subjects with ongoing ARIA-E at the time of data cutoff (also considered as unresolved) will be provided with the details of the event including the duration from onset to last follow-up.

For subjects with recurrent ARIA-E, a listing of study drug administration, MRI assessments, severity and symptomatic status of each event, and end-of-treatment reason (if present) will be provided.

Final V1.0

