4.5.3.5 Time to event analysis

Kaplan-Meier plot of time to first ARIA-E event will be produced based on safety MRI data. Time to event is calculated as date of the MRI assessment that initially detects ARIA-E event - date of first infusion (aducanumab or placebo) +1. Censor time for subjects without ARIA-E is calculated as date of last MRI assessment in the placebo-controlled period - date of first infusion (aducanumab or placebo) +1. Estimated proportion with ARIA-E and number of subjects at risk at selected timepoints will also be presented. The plot will be presented by treatment group stratified by ApoE status.

4.5.3.6 Subgroup analysis for protocol version 4

Due to the change in maximal dose from 6 mg/kg to 10 mg/kg for ApoE &4 carrier high dose group in protocol version 4, not all subjects have had opportunity to receive the protocol specified high dose (6 doses in titration before receive 10mg/kg) in the placebo-controlled period. Incidence of ARIA events and summary of first ARIA-E events tables will be provided for ApoE &4 carriers who were randomized to the high dose group, stratified by the expected number of doses at 10 mg/kg (categories of 0, 1-6, 7-13, 14, and a total column of having at least one dose) a subject would have received based on the first infusion date and the date consenting to protocol version 4. Randomization treatment groups will be used for this analysis.

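### The only summary of ARIA-E duration uses resolved events, so it tends to understate duration, more so for later events; a Kaplan-Meier time-to-resolution summary should be added

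*SAP*

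**What the plan says.** Section 4.5.3.3 of the placebo-controlled SAP specifies one table for first ARIA-E events and one for second and third events. The first-event table reports "number of resolved and unresolved events, duration of the resolved events". The recurrent-event table uses the same rule: "number of resolved and unresolved events, duration of the resolved events, time from first infusion in study (active or placebo) to onset". Both are based on the AE eCRF.

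The section then adds "A listing of subjects who withdrew from the study with unresolved ARIA-E", together with subjects whose ARIA-E is ongoing at data cutoff, "with the details of the event including the duration from onset to last follow-up". Section 3.5.3.3 of the LTE SAP repeats the tables and the listing.

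Section 4.5.3.1 fixes the end of an ARIA-E event, for duration based on MRI, as "the date of the MRI assessment that shows the complete resolution of this ARIA event". An event not seen to resolve has no end date.

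Section 4.5.3.5 plans a censored analysis, but for onset only: "Kaplan-Meier plot of time to first ARIA-E event will be produced based on safety MRI data". Subjects without ARIA-E are censored at their last MRI. Neither SAP plans the same for time to resolution.

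**The concern.** An event still open at withdrawal or data cutoff has a right-censored duration: it lasted at least as long as it was observed. Dropping it from the duration summary selects events by their own length, because a long event is more likely to outlast the remaining follow-up. A larger sample does not remove this.

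ARIA is the adverse event of special interest, and this line is the only summary of how long ARIA-E lasts, so it is likely to be read that way. The tables also place groups side by side, by dose group and ApoE status and by event rank. Second and third events necessarily start later and have less follow-up left, so they can look shorter than first events when nothing differs. The SAP already handles the matching problem for onset with Kaplan-Meier methods.

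**Working it through.** The SAP states no figure for ARIA-E duration, the unresolved share or their effect, so there is nothing to reproduce. The check covers the direction and plausible size of the bias.

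**Inputs from the SAP.** Section 2.1 gives "a 76-week placebo-controlled treatment period, and a safety follow-up (FU) period of approximately 18 weeks after the final dose", so follow-up is 76 + 18 = 94 weeks. Section 3 assumes 30% dropout, taken here as the upper value. Section 4.5.3.2 puts ARIA monitoring visits about every 4 weeks.

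**Assumed inputs.** Mean durations of 8, 12, 16 or 24 weeks; exponential, Weibull (shape 2) or lognormal shape (log-SD about 0.8); onset uniform over weeks 4-36 or 4-76; dropout of 0, 10 or 30% per 78 weeks, independent of duration.

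**Step 1: mechanism.** If the duration D is exponential with mean m, and c weeks of follow-up remain at onset with no dropout, then

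E[D | D ≤ c] = m − c·e^(−c/m) / (1 − e^(−c/m)).

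Take m = 12:
- Onset at week 36: c = 94 − 36 = 58 and e^(−58/12) = 0.0080, so 0.8% of events are open. Resolved-only mean = 12 − 58 × 0.0080/0.9920 = 11.5 weeks, 4% short.
- Onset at week 60: c = 94 − 60 = 34 and e^(−34/12) = 0.0588, so 5.9% are open. Resolved-only mean = 12 − 34 × 0.0588/0.9412 = 9.9 weeks, 18% short.

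The true duration is the same in both; only the time left differs.

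**Step 2: range.** 200,000 events were simulated per scenario, counting an event as resolved if D ≤ min(94 − onset, dropout time). Selected results in weeks, true value → resolved-only value:

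| Shape, mean | Onset (weeks) | Dropout | Open | Mean | Median | Kaplan-Meier median |
|---|---|---|---|---|---|---|
| Weibull, 8 | 4-36 | 0% | 0.0% | 8.0 → 8.0 (0%) | 7.5 → 7.5 (0%) | 7.5 |
| Lognormal, 12 | 4-76 | 10% | 4.4% | 12.0 → 10.8 (−10%) | 8.7 → 8.4 (−4%) | 8.7 |
| Lognormal, 16 | 4-76 | 30% | 11.5% | 16.0 → 13.3 (−17%) | 11.6 → 10.6 (−8%) | 11.6 |
| Weibull, 24 | 4-76 | 30% | 19.9% | 24.0 → 21.5 (−10%) | 22.5 → 20.1 (−11%) | 22.5 |
| Exponential, 24 | 4-76 | 30% | 21.2% | 24.0 → 16.3 (−32%) | 16.6 → 12.4 (−25%) | 16.6 |

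Across all scenarios 0-21% of events stayed open, the resolved-only mean was 0-32% short and the median 0-25% short. With a mean duration of 8 weeks, the mean was at most 7% short. The Kaplan-Meier median recovered the true median throughout.

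**Step 3: early against late events.** Both groups were given the same durations (lognormal, median 12 weeks, log-SD 0.75, rounded up to the next 4-week MRI; true mean 17.9 weeks) and 30% dropout.
- Onset weeks 4-36: 8% open, resolved-only mean 16.6 weeks (1 − 16.6/17.9 = 7% short).
- Onset weeks 50-86: 30% open, resolved-only mean 12.8 weeks (1 − 12.8/17.9 = 28% short).

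Later events look 1 − 12.8/16.6 = 23% shorter with no real difference. The 30% open here exceeds the Step 2 range because every onset is late.

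**The case against.** The strongest reply is that nothing is hidden. The number of unresolved events stands beside the duration in the same table, and the listing covers the two groups in question, withdrawal and data cutoff, with their observed time to last follow-up. The statistic is correctly labelled as the duration of resolved events. It is descriptive, and no test or estimated difference in duration is planned. All of that stands. A reader might infer that open events disappear from the report, or that a planned comparison is invalid; the SAP supports neither. What remains is that a count and a subject listing do not give a median duration.

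A reader might also infer a much larger bias, for example with about 40% of events open. That share needs an assumption such as censoring spread evenly over 0-40 weeks from onset, which does not fit about 94 weeks of follow-up. Section 4.5.2 adds that some subjects stay on study well beyond 18 weeks after their last dose. Nor should the range above be carried over to the LTE SAP: its 256-week treatment period gives extension participants far more time for resolution to be seen.

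Two further points hold. Section 4.1 says continuous summaries generally include the median, which is usually less affected than the mean. Kaplan-Meier estimation assumes that censoring is unrelated to event length. The simulation builds that in, so its agreement with the true median does not show robustness to withdrawal that depends on the event.

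**Conclusion.** The point holds as a minor one. The only duration summary in Section 4.5.3.3, and in LTE Section 3.5.3.3, is restricted to resolved events. It therefore tends to understate ARIA-E duration, and more so for later-starting, recurrent events. The direction follows from the definition of event end in Section 4.5.3.1 when withdrawal and cutoff are unrelated to event length. The size cannot be known from the SAP: the 0-32% shortfall in the mean and 0-25% in the median rest on assumed durations, onset times and dropout, and the effect vanishes if nearly all events resolve under observation. ARIA incidence, time to onset and the efficacy conclusions are unaffected.

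**What to change.** In Section 4.5.3.3 and LTE Section 3.5.3.3, add for each event rank (first, second, third) a Kaplan-Meier summary of time to resolution: median and 25th and 75th percentiles. The event is the MRI showing complete resolution; unresolved events are censored at the last MRI in the analysis period. State the data source, because these tables draw on the AE eCRF while the onset analysis uses safety MRI data. State the start date too, because Section 4.5.3.1 defines a different one for symptomatic events. Keep the resolved-only duration as a labelled line, with the counts and the listing unchanged.

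The cost is a few lines of text and a little extra analysis. The listing runs to last follow-up, which is not defined as the last MRI, so the censoring date may need its own derivation. The reported duration will be somewhat longer, and the text should acknowledge the assumption that censoring is unrelated to event length.

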4.5.3.4 Exposure adjusted analysis

Exposure adjusted incidence rate of ARIA-E events will be summarized based on safety MRI data. The exposure adjusted follow-up time is from the first dose until the initial occurrence of ARIA-E for those who experienced ARIA-E, and until the end of follow-up for those who did not. Since ARIA is an MRI finding, the day of the last MRI assessment in the placebo-controlled period will be used as the end of follow-up for those who didn't experience the event.

Study drug administration information prior to first ARIA-E onset will be summarized for ARIA-E subjects, including number of total infusions, number of infusions at each dose level (placebo, 1 mg/kg, 3 mg/kg, 6 mg/kg and 10 mg/kg), dose level of the last infusion, maximum dose level received, and cumulative dose as a continuous variable.

4.5.3.5 Time to event analysis

Kaplan-Meier plot of time to first ARIA-E event will be produced based on safety MRI data. Time to event is calculated as date of the MRI assessment that initially detects ARIA-E event - date of first infusion (aducanumab or placebo) +1. Censor time for subjects without ARIA-E is calculated as date of last MRI assessment in the placebo-controlled period - date of first infusion (aducanumab or placebo) +1. Estimated proportion with ARIA-E and number of subjects at risk at selected timepoints will also be presented. The plot will be presented by treatment group stratified by ApoE status.

4.5.3.6 Subgroup analysis for protocol version 4

Due to the change in maximal dose from 6 mg/kg to 10 mg/kg for ApoE &4 carrier high dose group in protocol version 4, not all subjects have had opportunity to receive the protocol specified high dose (6 doses in titration before receive 10mg/kg) in the placebo-controlled period. Incidence of ARIA events and summary of first ARIA-E events tables will be provided for ApoE &4 carriers who were randomized to the high dose group, stratified by the expected number of doses at 10 mg/kg (categories of 0, 1-6, 7-13, 14, and a total column of having at least one dose) a subject would have received based on the first infusion date and the date consenting to protocol version 4. Randomization treatment groups will be used for this analysis.

4.5.4 Clinical Laboratory Data

The following clinical laboratory parameters are assessed in the protocol and will be analyzed:

- o Hematology:
 - White blood cells (leukocytes), lymphocytes, neutrophils, monocytes, eosinophils, basophils
 - Red blood cells (erythrocytes), erythrocytes distribution width, erythrocytes mean corpuscular volume, erythrocytes mean corpuscular hemoglobin, erythrocytes mean corpuscular hemoglobin concentration

- Hemoglobin
- Hematocrit
- Platelet count
- Blood chemistry:
 - Liver: alanine aminotransferase (ALT), aspartate aminotransferase (AST), alkaline phosphatase (ALP), total bilirubin, direct bilirubin, gamma-glutamyl-transferase (GGT)
 - Renal: blood urea nitrogen (BUN), creatinine
 - Electrolytes: sodium, potassium, chloride, bicarbonate
 - Other: glucose, calcium, phosphorus, albumin, uric acid, lactate dehydrogenase (LDH), total protein
- o Urinalysis: specific gravity, potential of hydrogen (pH), color, blood, glucose, ketones, protein, white blood cells, red blood cells

4.5.4.1 Quantitative analyses

For numeric laboratory parameters, actual values, change from baseline and percent change from baseline will be summarized by visit. Number of evaluable subjects, mean, standard deviation, median, 25% and 75% quartiles, minimum and maximum values will be presented at each visit.

Plots of mean values (with standard error) for numeric laboratory parameters at each visit will be provided.

Listings of individual laboratory measurements by patients for all the parameters will be provided.

Visit windows for by visit summaries

For laboratory by visit summaries, the analysis visit should be defined using visit windows (see Table 7 below). If there is more than 1 value in the same analysis visit window for a certain parameter for a subject, then the closest record to the target visit day will be used for the by visit analysis. If there are 2 values in the same analysis visit window with the same distance from the target visit day for a certain parameter for a subject, then the record with the later date will be used for the by visit analysis. If there are 2 values on the same day for a certain parameter for a subject, then the record with the later time will be used for the by visit analysis.

Table 7: Visit Windows for Laboratory by Visit Summaries

Analysis visit	Target visit day	Analysis visit window
Baseline	1	Most recent non-missing pre-dose value
Week 24	169	[2, 252]
Week 48	337	[253, 420]
Week 72	505	[421, 525]

CONFIDENTIAL

The information contained herein may not be used, disclosed, or published without the written consent of Biogen MA Inc.

Final V1.0

Analysis visit	Target visit day	Analysis visit window			
Week 78	547	[526, the end day of the placebo-controlled period*]			
* The end day of the placebo-controlled period is the last day before the first infusion in LTE for					
subjects who enter L	TE and is the last day in	study for subjects who do not enter LTE			

4.5.4.2 Qualitative analyses

For all qualitative analyses, all values will be included (not just the "analyzed record" within each visit window in the quantitative analyses).

Shift analyses

Laboratory data will be summarized using shift tables where appropriate. Each subject's hematology, blood chemistry and urinalysis numeric values will be flagged as "low", "normal", or "high" relative to the normal ranges of the central laboratory or as "unknown" if no result is available. Each subject's urinalysis categorical values will be flagged as "positive" or "negative", or "unknown" if no value is available.

Shifts from baseline to high/low status will be presented for hematology, blood chemistry and urinalysis numeric parameters, and shifts from baseline to abnormal (positive) will be presented for urinalysis categorical parameters. Shift to low includes normal to low, high to low, and unknown to low; Shift to high includes normal to high, low to high, and unknown to high. Subjects need to have at least one post-baseline evaluation and a baseline value not low or high or positive (including missing) in order to be included in the analysis. A listing of laboratory normal ranges will be provided.

Grade analyses

Worst post-baseline grade will be summarized for each laboratory parameter in both exclusive way and cumulative way. Subjects need to have at least one post-baseline evaluation in order to be included in the analysis. Common Toxicity Criteria for Adverse Events v4.0.3 (CTCAE) published on 2010-06-14 will be used for grade determination. Grade determination is based solely on laboratory values not taking AEs into account.

Potentially Clinically Significant laboratory abnormalities analyses

For hematology, blood chemistry and urinalysis, the number of subjects with potentially clinically significant laboratory abnormalities post-baseline will be summarized for the parameters provided in Table 8. Subjects need to have at least one post-baseline evaluation and a baseline value not potentially clinically significant (including missing) in order to be included in the analysis.

Table 8: Criteria to Determine Potentially Clinically Significant (PCS) Laboratory Abnormalities

Clinical Laboratory Outlier Criteria			
Parameter name	PCS Low	PCS High	
HEMATOLOGY			

Final V1.0

Clinical Laboratory Outlier Criteria				
Parameter name	PCS Low	PCS High		
White blood cells	<3.0 x 10 ⁹ /L	$>16 \times 10^9/L$		
Lymphocytes	<0.8 x 10 ⁹ /L	>12 x 10 ⁹ /L		
Neutrophils	<1.5 x 10 ⁹ /L	>13.5 x 10 ⁹ /L		
Monocytes	N/A	>2.5 x 10 ⁹ /L		
Eosinophils	N/A	>1.6 x 10 ⁹ /L		
Basophils	N/A	>1.6 x 10 ⁹ /L		
Red blood cells	$\leq 3.5 \times 10^{12}/L$	\geq 6.4 x 10 ¹² /L		
Hemoglobin - Females	≤95 g/L	≥175 g/L		
Hemoglobin - Males	≤115 g/L	≥190 g/L		
Hematocrit - Females	≤32%	≥54%		
Hematocrit - Males	≤37%	≥60%		
Platelet count	≤75 x 10 ⁹ /L	≥700 x 10 ⁹ /L		
BLOOD CHEMISTRY				
Alanine aminotransferase (ALT)	N/A	>3 x ULN		
Aspartate aminotransferase (AST)	N/A	>3 x ULN		
Alkaline phosphatase (ALP)	N/A	>3 x ULN		
Total bilirubin	N/A	>1.5 x ULN		
Blood urea nitrogen (BUN)	N/A	≥10.7 mmol/L		
Creatinine	N/A	≥176.8 umol/L		
Sodium	≤126 mmol/L	≥156 mmol/L		
Potassium	≤3 mmol/L	≥6 mmol/L		
Chloride	≤90 mmol/L	≥118 mmol/L		
Bicarbonate	≤16 mmol/L	≥35 mmol/L		
Glucose	≤2.2 mmol/L	≥9.7 mmol/L		
Calcium	≤2 mmol/L	≥3 mmol/L		
Phosphorus	≤0.6 mmol/L	≥1.7 mmol/L		
Albumin	≤25 g/L	≥625 g/L		
Total protein	≤45 g/L	≥100 g/L		
URINALYSIS				
Glucose	N/A	≥++++		
Ketones	N/A	≥++++		
Protein	N/A	≥++		
ULN = upper limit of normal				

Potential serious hepatotoxicity

Potential serious hepatotoxicity is defined as ALT or AST > 3x ULN and total bilirubin > 2x ULN at any time post-baseline, not necessarily concurrent. A scatterplot of the maximum post-baseline ALT or AST value relative to ULN and maximum post-baseline total bilirubin value relative to ULN (not necessarily concurrent) for each subject will be provided. A line plot of ALT, AST, ALK and total bilirubin values over time for subjects with potential serious hepatotoxicity will be provided. In addition, subjects with ALT > 1x ULN, >3x ULN, >5x ULN, >10x ULN or >20x ULN, subjects with AST > 1x ULN, >3x ULN, >5x ULN, >10x ULN or >20x ULN, subjects with total bilirubin >1x ULN or >2x ULN, subjects with ALP >1x ULN or >1.5x ULN, and subjects with AST or ALT > 3x ULN post-baseline accompanied by concurrently elevated total bilirubin >1.5x ULN or > 2x ULN will be presented. Concurrent is defined as on the same day. A listing of subjects with potential serious hepatotoxicity will be provided.

Final V1.0

